6.5.7. Collection of medical history, demographic and lifestyle characteristics

Obtain the family medical history, demographic and lifestyle characteristics of the subject as required by the eCRF, by interviewing parent(s)/LAR(s) and/or reviewing the medical records and record data collected in the subject's eCRF. This includes family history of respiratory disease, living environment and household composition, breastfeeding, passive smoking and day-care attendance.

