6.6.4. Potential risk factors for / occurrences of wheeze and asthma

6.6.4.1. Data collected from the parent(s)/LAR(s)

The following data are to be collected by interviewing the parent(s)/LAR(s). Refer to the SPM *for additional details*

Genetic History

- Family history of asthma
- *Family* history of allergies

Child/subject variables of interest

- Past or current allergies
- Exposure to environmental/household or other risk factors for asthma
- Child's activity levels
- Potential signs/symptoms of asthma
- Episodes of wheeze, asthma, or troublesome lung symptoms since the end of the primary study and their associated care
- Medications taken to *prevent or* treat *asthma, wheeze or troublesome* lung symptoms

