3.3. Tertiary objectives

In a cohort of infants followed-up from birth up to 2 years of age;

- To explore the association of co-infections with the incidence of RSV-associated LRTI and/or severe LRTI (as determined by the LRTI case definition and severity scale) using xTAGTM respiratory viral panel (RVP) fast assay.
- To explore the association of RSV and other respiratory viruses with the incidence of LRTI and/or severe LRTI (as determined by the LRTI case definition and severity scale) using xTAGTM RVP Fast assay.
- To explore the association of RSV viral load with the incidence of RSV-associated RTI, LRTI and/or severe LRTI (as determined by the LRTI case definition and severity scale).
- To explore the impact of changes to the symptoms and threshold levels of symptoms in the LRTI case definition and severity scale.

200150 (EPI-RSV-005 BOD)

Statistical Analysis Plan Amendment 1 Final

- To assess the impact of potential RSV risk factors (e.g. complications at birth, family history of respiratory disease, living environment and household composition, breast feeding, passive smoking, day care attendance) on the incidence and severity of RSV-associated LRTI.
- To explore the impact of variations in cord-blood sample collection variables on the stability of test results.
- To assess the natural decay of maternal antibody levels using a single follow-up blood sample collected from a randomly selected sub-cohort of subjects at 2, 4, 6, 12, 18 and 24 months.

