6.1.4.4. Family history of respiratory disease

The subject will be considered to have family history of respiratory disease if at least one of its first degree relative (i.e. mother father or sibling) has respiratory disease.

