6.6.3. Analysis of tertiary objectives: potential risk factors for RSV disease

For this objective, the analysis will be based on PPS.

The incidence, overall and by country, of first events of RSV-LRTI, RSV severe LRTI, RSV non severe LRTI (WHO definition) will be analysed using a Cox regression.

The following risk factors will be considered in the model:

- General:
 - Country of birth
 - Gender (as recorded in demography of extension phase)
 - Time of birth relative to the transmission season (see section 6.1.4.5)
- Characteristics at birth:
 - Gestational age at birth (see details section 6.1.4.1)
 - Birth weight (see details section 6.1.4.2)
 - Apgar at 5 mins of age (see details section 6.1.4.3)
 - Caesarian section
- Family history:
 - First degree relative with family history of asthma (see details section 6.1.4.4)
- Living environment and household composition:
 - Highest education level of the mother (see details section 6.1.4.6)
 - Highest education level of the father (see details section 6.1.4.6)
 - Number of people living in the household at month 3 (see details section 6.1.4.7)
200150 (EPI-RSV-005 BOD)

- Statistical Analysis Plan Amendment 1 Final
- Number of other children (<18 years old) living in the household at month 3 (see detail section 6.1.4.8)
- Subject in regular close contact with toddlers at month 3
- The child live in a surrounding where people smoke daily at month 3
- Breast feeding *

* Time dependent covariate; status is yes of subject ever breastfed from DOB until the end of breastfeeding given in the surveillance visit. Last day of month will be imputed for any partial date of breastfeeding end date.

As described in the section 11.1.5, covariates with univariate p-value less than 0.1 will be included in the multivariable model. The number of covariates included in the model will depend on the number of events (at least 10 events per covariates).

Please note that the multivariable model will be performed only if the number of events is sufficient (at least 10 events per covariates). In addition, depending on the data, other models could be explored or the model could be simplified.

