11.1.5. Cox regression models

Cox regression models will be performed for the univariate analyses in order to obtain unadjusted hazards ratios of the determinants of interest.

200150 (EPI-RSV-005 BOD)

Statistical Analysis Plan Amendment 1 Final

In addition, a multivariable Cox regression model will be performed in order to estimate the relative contribution of each potential risk factor adjusting for the simultaneous effects of the other covariates. The model will include: time-independent covariates (e.g., country, gender etc.) and time-dependent covariates, breast feeding. Covariates selection will be done using statistical significance. Potential risk factors will be included in the multivariable models if univariate p-value will be less than 0.1.

The Table 15 details the time dependent status of the potential risk factors:

Table 15Time dependent status of the covariates

Potential risk factor	Time-dependent
Country of birth	No
Gender	No
Birth period	No
Gestational age at birth	No
Birth weight	No
Apgar at 5 mins of age	No
First degree relative with family history of asthma	No
Quartiles of cord blood maternal antibodies for RSV A	No
Quartiles of cord blood maternal antibodies for RSV B	No
Highest education level of the mother	No
Highest education level of the father	No
Number of people living in the household at month 3	No
Number of other children (<18 years old) living in the household at month 3	No
Subject in regular close contact with toddlers at month 3	No
The child live in a surrounding where people smoke daily at month 3	No
Breast feeding	Yes

Results from the multivariable Cox model will include hazards ratios (with 95% CI).

The number of covariates included in the model will depend on the number of events (at least 10 events per covariates).

Please note that the multivariable model will be performed only if the number of events is sufficient (at least 10 events per covariates). In addition, depending on the data other models could be explored or the model could be simplified.

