RSV-B maternal antibodies levels in cord blood	Seronegative					
	Seropositive					
	Missing					
RSV-A maternal antibodies levels in cord blood	Q1 (min - max)					
	Q2 (min - max)					
	Q3 (min - max)					
	Q4 (min - max)					
RSV-B maternal antibodies levels in cord blood	Q1 (min - max)					
	Q2 (min - max)					
	Q3 (min - max)					
	Q4 (min - max)					
RSV-A maternal antibodies levels in cord blood	Continuous					
RSV-B maternal antibodies levels in cord blood	Continuous					
Country	Argentina					
	Missing					
Gender	Female					
	Male					
	Missing					
	Within transmission					
Time of birth	season			ļ		
	Outside transmission					
	season					

200150 (EPI-RSV-005 BOD)

		Statistic	al Ana	vsis Plar	1 Amendme	nt 1 Final
Characteristics	Category	Number of Observations Used in the model	Event	Hazard ratio (95% Cl)	p-value	Global p- value
Gestational age at birth	<= 36 weeks					
	>36 weeks					
Birth weight	< 2.5 kg					
	>= 2.5 kg					
Apgar at 5 mins of age	0-3					
	4 – 6					
	>= 7					
	Missing					
First degree relative with FH of	Yes					
asthma	No					
	Missing					
Highest education level of the	Yes					
mother: Higher education /	No					
university	Missing					
Highest education level of the	Yes					
father: Higher education /	No					
university	Missing					
Number of people living in the	1-3					
household at Month 3	4-6					
	>=7					
Number of other children (<18	0					
years old) living in the	1-2					
household at Month 3	>=3					
Subject in regular close contact	Yes					
with toddlers at Month 3	No					
	Missing					
The child live in a surrounding	Yes					
where people smoke daily at	No					
Month 3	Missing					
Breast feeding*	Yes					
, č	No					
	Missing					

Hazard ratio (95% CI) = Hazard ratio and 95% confidence intervals

RSV-A / RSV-B seronegative samples are defined as samples with RSV-A / RSV-B maternal antibodies levels in cord blood < LLOQ

RSV-A / RSV-B seropositive samples are defined as samples with RSV-A / RSV-B maternal antibodies levels in cord blood >= LLOQ

* Time-varying covariates :

- Number of observations used in the model = Number of observations which appeared at least once in the followup period. One observation can be counted in several modalities.

- Event = The number of events corresponds to the value recorded at the most recent visit before the endpoint.

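### The family-history covariate is labelled asthma in the SAP's Cox models, but the rule it is sent to codes any respiratory disease in a first-degree relative

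*SAP*

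**What the plan says.** The risk-factor model in SAP 6.6.3 has one family-history item: "First degree relative with family history of asthma (see details section 6.1.4.4". The section it points to, SAP 6.1.4.4, is headed as family history of respiratory disease. It counts a child as positive when "at least one of its first degree relative (i.e. mother father or sibling) has respiratory disease".

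The asthma wording appears in four other places:
- the covariate list for the cord-blood antibody models in SAP 6.9.1, without a cross-reference;
- Table 15 in SAP 11.1.5, as "First degree relative with family history of asthma";
- Template 17, where the row label begins "First degree relative with FH of" and ends with asthma on the next table line;
- Templates 43, 44 and 45, with the same row.

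The tertiary objective served by the risk-factor model (SAP 3.3, protocol 2.1.3) gives as examples "complications at birth, family history of respiratory disease, living environment and household composition". The tertiary endpoint (SAP 4.3, protocol 9.1.3) also names respiratory disease. For the baseline interview, protocol 6.5.7 states: "This includes family history of respiratory disease, living environment and household composition, breastfeeding, passive smoking and day-care attendance". The protocol lists "Family history of asthma" as a data item only in 6.6.4.1, which covers the extension study.

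**The concern.** One table row has two definitions. Asthma is only one of the respiratory diseases that a parent or sibling may have, so a child can be positive under 6.1.4.4 and negative for the printed label.

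Each way of programming the row leaves a fault:
- **Following the cross-reference.** The tables print a hazard ratio labelled asthma that belongs to any respiratory disease in the family.
- **Following the label.** The factor named in the objective is not assessed, and the programmer has neither a derivation nor a named source variable for asthma.

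The coding also matters for model selection, because "covariates with univariate p-value less than 0.1 will be included in the multivariable model", subject to at least 10 events per covariate. Two codings of one item can fall on opposite sides of that threshold. Template 4, the baseline table, has no family-history row, so the report would not show which coding had been used.

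**Working it through.** The plan gives no figure for this covariate, so there is nothing to reproduce. The main check is a comparison of the texts.

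**Step 1: what each place says.**

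| Place | Exposure named |
|---|---|
| SAP 3.3 and protocol 2.1.3 (objective) | respiratory disease |
| SAP 4.3 and protocol 9.1.3 (endpoint) | respiratory disease |
| Protocol 6.5.7 (Visit 2 data) | respiratory disease |
| SAP 6.1.4.4 (derivation) | respiratory disease |
| SAP 6.6.3 (covariate, pointing to 6.1.4.4) | asthma |
| SAP 6.9.1 (covariate) | asthma |
| SAP Table 15 | asthma |
| SAP Templates 17, 43, 44, 45 | asthma |
| Protocol 6.6.4.1 (extension data) | asthma |

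**Step 2: is it a declared change?** SAP section 9 lists departures from the protocol, including the move from Poisson to Cox regression for this same analysis. It does not mention a change from respiratory disease to asthma. The SAP contains no asthma-specific derivation.

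**Step 3: can the size be worked out?** Only by assumption. Let pa be the share of children with an asthmatic first-degree relative, and po the share whose relatives have only other respiratory disease. Let HRa and HRo be the corresponding hazard ratios against children with neither. Treating hazards as simple weighted averages:

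- any respiratory disease versus none: (pa × HRa + po × HRo) / (pa + po)
- asthma versus no asthma: HRa / {[(1 − pa − po) + po × HRo] / (1 − pa)}

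For pa = po = 0.10, HRa = 1.5 and HRo = 1.0, the first gives (0.15 + 0.10) / 0.20 = 1.25 and the second 1.5 / (0.90 / 0.90) = 1.50. If HRo is 1.5, the first gives (0.15 + 0.15) / 0.20 = 1.50 and the second 1.5 / (0.95 / 0.90) = 1.42.

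| pa | po | HRa | HRo | Asthma coding | Any-respiratory coding |
|---|---|---|---|---|---|
| 0.10 | 0 | 1.5 | any | 1.50 | 1.50 |
| 0.10 | 0.10 | 1.5 | 1.0 | 1.50 | 1.25 |
| 0.10 | 0.10 | 1.5 | 1.25 | 1.46 | 1.38 |
| 0.10 | 0.10 | 1.5 | 1.5 | 1.42 | 1.50 |
| 0.10 | 0.20 | 1.5 | 1.0 | 1.50 | 1.17 |
| 0.10 | 0.20 | 1.5 | 1.5 | 1.35 | 1.50 |

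With HRo = 1.0, pa of 0.10 or 0.20 and po from 0.05 to 0.20, the any-respiratory value runs from 1.40 down to 1.17 when HRa is 1.5, and from 1.80 down to 1.33 when HRa is 2.0. With HRo equal to HRa the order reverses. With po = 0 the two codings are the same variable. All these inputs are assumptions.

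**The case against.** The best defence of the text is that the cross-reference may serve only to define a first-degree relative (mother, father or sibling), with the label supplying the disease. That is possible, so wrong programming is a risk and not a certainty. The heading and sentence of 6.1.4.4 weigh against it, since both name respiratory disease. On that reading, too, the objective's factor is dropped without being recorded in section 9. SAP 6.9.1 has no cross-reference, so the argument from following the pointer is direct only for 6.6.3.

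The defence can also say that the reach is small: one covariate, given as an example in the objective, in analyses that SAP section 7 declares descriptive. That stands and limits the priority of the point. It does not make the row label correct.

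A reader might infer three stronger things that the documents do not support:
- **That the printed hazard ratio would be diluted.** This needs other respiratory disease to carry a lower hazard ratio than asthma. At equal hazard ratios the any-respiratory figure is not attenuated, and the asthma figure is the lower of the two.
- **That the adjustment set must change.** Entry depends on the univariate p-value and the events limit, and in 6.9.1 the covariates are only candidates. The item could be left out under both codings.
- **That both versions can be derived from Visit 2 data.** Protocol 6.5.7 names only respiratory disease; nothing shows that the baseline form separates asthma.

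**Conclusion.** The inconsistency is real and internal to the SAP: 6.6.3 itself sends the asthma covariate to a rule that codes any respiratory disease. As written, the row labelled asthma would report a different, broader exposure. The direction and size of the difference cannot be determined from the documents; the figures above only show that it may be nil, downward or upward. The choice of coding could decide whether the covariate enters a multivariable model, but no such change is demonstrated.

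The documents do not establish which wording was intended. The objective, endpoint, Visit 2 data collection and derivation all favour respiratory disease, which makes the asthma label the likelier slip.

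The scope is one covariate in the tertiary risk-factor models and one optional adjuster in the secondary antibody models. The co-primary results are unaffected. It should be corrected before programming, but it does not threaten the study's main conclusions.

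**What to change.** Use one definition everywhere.

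- **Default.** Keep the objective's factor, any respiratory disease in a first-degree relative, as 6.1.4.4 derives it. Relabel the covariate in SAP 6.6.3, 6.9.1, Table 15 and Templates 17, 43, 44 and 45, and name the source variable.
- **If asthma is intended.** Give it its own derivation in 6.1.4.4 and state whether the source is Visit 2 or the extension. Record the departure from the protocol in section 9. If the source is the extension, state the expected missingness: only re-consenting children contribute, and the footnote to Template 4 already reports missing gender data for a variable collected there.
- **Optional.** Add asthma as a separate covariate only if the Visit 2 data identify it. It is nested within respiratory disease, so the SAP would need to say how the two are handled under the limit of 10 events per covariate.

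The default costs label edits only, with no new data. The asthma route needs one derivation, a section 9 entry and, if the source is the extension, acceptance of a smaller informative sample.

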6.1.4.5. Time of birth relative to the transmission season

The transmission season period is defined:

- from April to September in the North hemisphere
- from October to March in the South hemisphere
- all year long in the tropical hemisphere

A summary of transmission season is displayed in the following table.

200150 (EPI-RSV-005 BOD)

				,
Statistical	Analysis	Plan	Amendment	1 Final

Country	Hemisphere	Transmission season period
Canada	North hemisphere	April 1 to September 30
United States	North hemisphere	April 1 to September 30
Finland	North hemisphere	April 1 to September 30
Argentina	South hemisphere	October 1 to March 31
South Africa	South hemisphere	October 1 to March 31
Thailand	Tropical hemisphere	All year long
Bangladesh	Tropical hemisphere	All year long
Honduras	Tropical hemisphere	All year long

Table 10Summary of transmission season by country

All subjects from tropical hemisphere will be considered to be born within the season.

Subjects from North hemisphere will be considered to be born within the season if they are born between April and September. Subjects from South hemisphere will be considered to be born within the season if they are born between October to March.

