1. INTRODUCTION

1.1. Background (Amended 15-DEC-2017)

1.1.1. RSV

Respiratory syncytial virus (RSV) is an important cause of respiratory diseases. RSV is a highly contagious seasonal pathogen that is transmitted from person-to-person via direct or close contact with contaminated secretions, including respiratory droplets or fomites [Canducci, 2008]. RSV belongs to the family *Paramyxoviridae* and is one of the only two human pneumoviruses that have been currently recognized (the other being metapneumovirus). There are two major genetic RSV subtypes, A and B. These subtypes co-circulate, and the predominance of one over the other varies by year and geographic location [Graham, 2011].

RSV is found across the globe with incidences varying between countries and regions and even within a country or a region over multiple seasons. In areas of the inner tropics with perennial high rainfall, RSV seasonality is less clear-cut. Countries close to the equator have a distinct pattern of RSV transmission, with most cases appearing in one half of the year, but not in the other. But neither temperature nor rainfall appears to be the main determinant of the timing of these outbreaks [Weber, 1998]. Seasonal epidemics of RSV occur most frequently in the cold season in regions with temperate and Mediterranean climates and in the rainy season in tropical countries with seasonal rainfall. Roughly the RSV season runs from October to March in the temperate areas of the Northern Hemisphere (NH) and from May to September in the Southern Hemisphere (SH). But the exact timing of RSV circulation varies by geographic location and also by year [Mullins, 2003; Weber, 1998; Law, 2002].

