- The recruitment will be performed using a first application of SBIR where subjects will be entered on obtaining ICF and recruitment is controlled on the monthly recruitment rate. The aim is to attain a reasonably stable number of subjects per month over the full recruitment period in order to achieve an equal spread in the age of subjects at first exposure to an RSV season. Recruitment will be actively controlled through the SBIR system on country level according to agreed targets, actual recruitment rates, and further recruitment potential, so as to achieve a sufficient population on a regional level. With concurrent recruitment across the globe (with different seasonality) and an intended, steady recruitment over 18 months, the following population is to be included;
 - Subjects from NH during first 6 months
 - Subjects from SH during first 6 months
 - Subjects from NH during second 6 months
 - Subjects from SH during second 6 months
 - Subjects from NH during third 6 months; repeat of first 6 months NH
 - Subjects from SH during third 6 months; repeat of first 6 months SH

 In case recruitment is extended beyond 18 months, subjects recruited in the fourth 6 month period are a repeat to those recruited during the second 6 month period

Figure 3 RSV seasons in Northern and Southern Hemispheres

NH=Northern hemisphere, SH=Southern Hemisphere. Figure assumes equal recruitment targets on both hemispheres (which is not a requirement for the study).

Figure A represents recruitment in the NH and assumes RSV seasons running from November to April relative to a currently estimated time point 0 in Nov 2013.

Figure B represents recruitment in the SH and assumed RSV seasons running from May to October relative to a currently estimated time point 0 in Nov 2013.

Recruitment on both Hemispheres will include a period of 'On Season' recruitment and a period of 'Off Season' recruitment and a third period of recruitment matching the first period.

An interim analysis data lock is scheduled after 1.5 years or in June 2015, whichever occurs first.

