- An adequate response is obtained on non-live contact (e.g. return text message or return email). Any non-live contact that is not responded to after a maximum of 2 reminders within the course of 2 days should be followed up with a live contact.

Active surveillance is to occur at a defined frequency dependent on the known RSV seasonality.

• *RSV* has a typical winter/monsoon seasonality. The peak rates of *RSV* occur at different times on the Northern and Southern Hemisphere. The tropical regions are generally known to have little or no seasonality.

For this reason, an active surveillance schedule will usually be applied based on the known or expected RSV seasonality for each study country/site.

- 12 annual contacts One monthly contact in all the regions.
- At least 4 seasonal contacts An intermediate contact in the fourknown/expected peak months, depending on the RSV seasons in the country/site. More intermediate contacts may be scheduled if deemed necessary by the investigator.

Outside the scheduled active surveillance contacts, each country/site can employ additional activities to enforce active and passive surveillance at their discretion. These activities can be tailored to best meet the local situation (e.g. reminders, community consultation sessions, additional in-person subject support visits, etc.).

TIMING AND REQUIREMENTS FOR CONTACT

- Active surveillance contacts are scheduled compared to the calendar week (Sat-Sun) of enrollment into the study. So regardless of the day of birth, the first Sunday after birth is Week 1 in the surveillance schedule.
- Seasonal contacts can occur anytime during the season they are scheduled to occur. A minimum of three attempts, occurring on at least two different working days should be made.
- Monthly contacts should occur in the first two weeks of the calendar month. A minimum of six attempts, occurring on at least four different working days spread over two subsequent weeks should be made to make contact for monthly surveillance contacts.

DISCONTINUATION OF ACTIVE SURVEILLANCE

All reasonable efforts should be made to conduct all active surveillance contacts in line with the schedule mentioned above. However, subjects' parent(s)/LAR(s) of the subject may not be available for active surveillance for a period of time.

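### SAP 6.1.4.5 and Table 10 reverse the RSV transmission season in the five temperate countries, so Template 12's season rows and the birth-season coding are wrong

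*SAP*

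**What the plan says.** SAP 6.1.4.5 defines the transmission season as "from April to September in the North hemisphere" and "from October to March in the South hemisphere", and as the whole year in the tropical countries. It codes birth season from the same months: "Subjects from North hemisphere will be considered to be born within the season if they are born between April and September". Table 10 applies this to Canada, the United States and Finland (April–September) and to Argentina and South Africa (October–March). The footnotes of Templates 4 and 12 repeat it, and there the northern season is tied to 2014, although Table 10 gives no year.

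The protocol says the reverse in three places:

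- Section 1.1.1: "Roughly the RSV season runs from October to March in the temperate areas of the Northern Hemisphere (NH) and from May to September", where the second range refers to the South. It adds: "Seasonal epidemics of RSV occur most frequently in the cold season in regions with temperate and Mediterranean climates".
- Appendix C, Figure 3: "Figure A represents recruitment in the NH and assumes RSV seasons running from November to April" and "Figure B represents recruitment in the SH and assumed RSV seasons running from May to October".
- Appendix E, on the active surveillance schedule: RSV "has a typical winter/monsoon seasonality".

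Three planned items use the SAP definition: the split of the first 6 months of life into at most 3 or more than 3 months in season (SAP 6.3, Template 12); the born-in-season row of Template 4; and the birth-season covariate, listed for the risk-factor Cox model (SAP 6.6.3, Template 17) and optional in the cord-blood antibody models (SAP 6.9.1).

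**The concern.** The SAP assigns the warm half of the year to the temperate countries, where the protocol describes a cold-season disease. No harmless reading fits. A pre-season birth window is ruled out because SAP 6.3 uses the same term to count months of follow-up spent in season. A deliberate change is ruled out because SAP section 9 lists many departures from the protocol and this is not among them. The months recur in the text, the table and two footnotes, so a programmer following the SAP would implement them.

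Template 12 is at stake first. SAP section 9 drops the birth-period subgroup and puts the 3-month split in its place as the season breakdown of co-primary incidence. As written, it would tend to show less RSV disease in infants with more season exposure, and would contradict the calendar-month case counts in Template 16.

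**Working it through.** **1. Months side by side**

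| | SAP | Protocol 1.1.1 | Protocol Appendix C |
|---|---|---|---|
| North | Apr–Sep | Oct–Mar | Nov–Apr |
| South | Oct–Mar | May–Sep | May–Oct |

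Against 1.1.1 the SAP season shares no month in either hemisphere. Against Appendix C it shares one (April North, October South). Calendar months coded opposite to the protocol:

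- North: 12 of 12 (1.1.1) or 10 of 12 (Appendix C).
- South: 11 of 12 (1.1.1; April is in neither season) or 10 of 12 (Appendix C).

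**2. Share of infants in the wrong row**

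Assumption: births uniform over the year. Each birth date was classified under the SAP calendar and under each protocol calendar.

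- Birth-season label (Template 4 and the Cox covariate): 10/12 = 83% wrong under Appendix C; 12/12 = 100% (North) and 11/12 = 92% (South) under 1.1.1.
- Template 12 row (in-season time summed over the first 6 months and cut at 3 months): 83% wrong under Appendix C; about 100% (North) and 91% (South) under 1.1.1.

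**3. Real exposure in the Template 12 rows, Appendix C taken as true**

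| Row | Mean in-season months, SAP coding | Mean in-season months, correct coding |
|---|---|---|
| at most 3 | 4.3 | 1.5 |
| more than 3 | 1.7 | 4.5 |

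The reversal does not depend on the calendar chosen. For 12 northern cold seasons (starting September to December, lasting 4 to 6 months), the SAP's lower row always has the more in-season time: 2.7–4.5 months against 0.7–2.2.

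**4. Illustrative incidence rates**

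Assumptions: first-episode hazard of 0.4 per year in season and 0.4/R out of season, over 0–6 months. Rates are expected first episodes divided by expected person-years; Appendix C is taken as true.

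| R | Correct ratio, >3 vs ≤3 | Ratio under SAP coding |
|---|---|---|
| 3 | 1.67 | 0.64 |
| 5 | 2.00 | 0.55 |
| 10 | 2.39 | 0.47 |
| 20 | 2.66 | 0.43 |

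At R = 5 the correct rows are 16.0 (≤3) and 32.0 (>3) per 100 person-years; the SAP rows would be 30.8 and 16.9. Across the 12 calendars of step 3, the SAP-coded ratio at R = 5 is 0.45–0.70.

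The 0.4 is compatible with protocol section 9.3. Eight times 16.9–44.1 per 1000 gives an average of 0.14–0.35 per year under 6 months. With half of the time in season, the in-season rate is 2 × average × R/(R+1): from 2 × 0.135 × 3/4 = 0.20 to 2 × 0.353 × 20/21 = 0.67. Across that range the SAP-coded ratios stay at 0.64–0.43.

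**5. Cox birth-season covariate, one northern country, R from 3 to 20**

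| Window | Correct ratio | SAP coding, Appendix C true | SAP coding, 1.1.1 true |
|---|---|---|---|
| 0–2 months (6.9.1, optional) | 1.67–2.68 | 0.47–0.21 | 0.60–0.37 |
| 0–5 months (6.9.1, optional) | 1.02–1.03 | 0.74–0.58 | 0.98–0.97 |
| 2 years (6.6.3) | 1.00–1.02 | 0.98–0.97 flat hazard; 0.87–0.78 with hazard falling by age as in protocol Table 12 | 0.98–1.00 |

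In the model across all countries, tropical infants are always coded in season. The univariate screen at p < 0.1 therefore pools them with the wrong temperate group, and the error there is not a simple reciprocal.

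**The case against.** The calendar contradiction itself is hard to dispute. The case on the other side is about weight and precision.

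- **Reach.** The affected items are one breakdown, one baseline row and one covariate in a descriptive plan without hypothesis tests. Template 12 also omits the endpoint named in the co-primary objective, RSV RTI with suspected lower-tract involvement. This stands, and it limits the claim.
- **Noise.** Template 12 prints two rates with intervals per country, not a ratio. With 2400/8 = 300 infants per country, 150 per row, and the R = 5 rates, expected first episodes are 150 × (1 − exp(−0.308 × 0.5)) ≈ 21 and 150 × (1 − exp(−0.169 × 0.5)) ≈ 12, with overlapping exact intervals. At one-eighth of those rates the hospitalization rows would hold about 3 and 2 events. So the reversal is one of expected direction and need not appear in every country. Small counts do not excuse wrong row labels.
- **The 2014 footnotes.** Read literally, with births from November 2013 to April 2015, the share of northern infants in the wrong Template 12 row falls to about 72% (Appendix C) or 78% (1.1.1). The direction survives.
- **Cox model.** Over 2 years, the window of the 6.6.3 model, the distortion is near null unless Appendix C is the true calendar and hazard falls with age. This stands.
- **Which calendar.** The protocol gives two and says that timing varies by place and year. That is a fair reason not to insist on one, but neither puts the season where the SAP does.

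**Conclusion.** The concern holds. The SAP season is the reverse of the protocol's for Canada, the United States, Finland, Argentina and South Africa, and the change is undeclared. Followed as written, it puts 83% to about 100% of temperate-country infants in the wrong Template 12 row on a recurring calendar, reverses the expected direction of that table, mislabels the Template 4 row and miscodes the Cox covariate. The shares assume only uniform births; the rate ratios also rest on the assumed hazards. For the Cox covariate the harm is inversion over 0–2 months, where the covariate is optional. Over 0–5 months and 2 years there is almost no true effect to invert, though the wrong coding can create a spurious one if Appendix C is the true calendar.

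This is a required correction, but it does not threaten the main co-primary estimates. Overall and by-country incidence rates, proportions affected, Kaplan-Meier curves, Template 16 and the tropical countries are unaffected. No claim is made about the antibody hazard ratio.

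**What to change.** - Replace the months in SAP 6.1.4.5, Table 10 and the footnotes of Templates 4 and 12 with one stated calendar consistent with the protocol. Appendix C (North November–April, South May–October) is the natural default because recruitment was designed around it. A justified country-level cold-season calendar is also acceptable, if listed in SAP section 9.
- Delete 2014 from both footnotes so that the calendar applies in every year.
- Re-derive birth in season and months in season over the first 6 months of life. Leave the tropical rule unchanged.
- In SAP 6.9.3, state that off-season means outside that calendar. The section cites no calendar, so no error is claimed there. Under the all-year tropical rule the sensitivity analysis contains only temperate infants whichever calendar is used, but the current 6.1.4.5 would select mainly those born in the protocol's season.

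The cost is wording in one section, one table, two footnotes and one clause, plus two re-derived variables. No new data are needed.
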